6.4 STUDY INTERVENTION/EXPERIMENTAL MANIPULATION ADHERENCE

The major assumption is that patients will complete the intervention program to which they are randomly assigned. Although we have implemented several methods to promote engagement and limit dropout (e.g., health coaches), digital interventions often experience high attrition over time with few participants completing all assigned modules. We will track the reasons for noncompletion and seek patterns (e.g., moved away, died, started working and became too busy, people with higher cognitive level lost interest) that are amenable to statistical analysis of the missing data.

Quarterly assessments will be made of data quality and timeliness, participant recruitment, accrual and retention, participant risk/benefit ratio, protection of confidentiality of information, and any other factors that affect the study. The IRB will be informed immediately on a case by case basis, of any adverse outcomes, while requests for modifications of the protocol will be submitted to the IRB on a quarterly basis. Confidentiality of the data and the results of monitoring will be protected.

Parameters to be Monitored. The following progress will be monitored throughout the course of the research to ensure the safety of subjects as well as the integrity and confidentiality of their data.

- An evaluation of the progress of the research study, including subject recruitment and retention, and an assessment of the timeliness and quality of the data.
- A review of collected data (including adverse events, unanticipated problems, and subject withdrawals), to determine whether there is a change to the anticipated benefit-to-risk assessment of study participation and whether the study should continue as originally designed, should be changed, or should be terminated.
- An assessment of external factors or relevant information (e.g., pertinent scientific literature reports or therapeutic development, results of related studies) that may have an impact on the safety and study participants or the ethics of the research study.
- A review of study procedures designed to protect the privacy of the research subjects and the confidentiality of their research data.

The principal investigator will review the outcome and adverse event data to determine whether there is any change to the anticipated benefit-to-risk ratio of study participation and whether the study should continue as originally designed or should be re-evaluated and changed. The investigator will promptly report any unanticipated problems that occur during the conduct of the study according to the reporting criteria and timelines under the current IRB policies.

6.5 CONCOMITANT THERAPY

6.5.1 RESCUE THERAPY

N/A

7 STUDY INTERVENTION/EXPERIMENTAL MANIPULATION DISCONTINUATION AND PARTICIPANT DISCONTINUATION/WITHDRAWAL

7.1 DISCONTINUATION OF STUDY INTERVENTION/EXPERIMENTAL MANIPULATION

Throughout the course of the research the principal investigator will review collected data (including adverse events, unanticipated problems, and subject withdrawals), to determine whether there is a change to the anticipated benefit-to-risk assessment of study participation and whether the study should continue as originally designed, should be changed, or should be terminated.

7.2 PARTICIPANT DISCONTINUATION/WITHDRAWAL FROM THE STUDY

A participant may be discontinued from study treatment at any time if the participant or the investigator feels that it is not in the participant's best interest to continue. The following is a list of possible reasons for study treatment discontinuation:

- Participant withdrawal of consent (or assent)
- Participant is not compliant with study procedures
- Adverse event that in the opinion of the investigator would be in the best interest of the participant to discontinue study treatment
- Protocol violation requiring discontinuation of study treatment

If a participant is withdrawn from treatment due to an adverse event, the participant will be followed and treated by the investigator until the abnormal parameter or symptom has resolved or stabilized. All participants who discontinue study treatment should come in for an early discontinuation visit as soon as possible and will be encouraged to complete all remaining scheduled assessments (Pain Interference measure will be prioritized). All participants are free to withdraw from participation at any time, for any reason, specified or unspecified, and without prejudice. Reasonable attempts will be made by the investigator to ascertain a reason for participant withdrawals. The reason for the participant's withdrawal from the study will be specified in the participant's source documents.

7.3 LOST TO FOLLOW-UP

Intervention engagement and health coach contacts. Patients who stop reporting data in the intervention will receive inquiry text messages or a phone call (Health Coach Protocol). Since participation in the study is completely voluntary, patients may choose to discontinue the intervention at any time. During the study, participants are encouraged to have weekly check-ins with health coaches. This can be in the form of a message via the health app where there is at least one response from the participant. Failure to check in with health coach will not affect enrollment in the study; however, health coaches will reach out per the health coach protocol to solicit a response from participants.

Follow-up assessments. The study sites will take preventive measures to avoid a subject's being lost to follow-up (e.g., document different ways of contact such as telephone number,

email address, etc.). Each week, participants will complete a depression (PHQ-9) and anxiety (GAD7) symptoms questionnaire. At 1 and 4 weeks only, participants will also complete measures of Self-efficacy (SCSES), stigma, pain interference (PROMIS), and quality of life (ASCQ-ME).

Completion of the questionnaires is a required component of the study. Not completing questionnaires within 2 weeks of the due date is considered a missed follow-up. In the event that a follow-up assessment is not completed, every possible effort will be made by study site personnel to contact the subject. For each follow-up, at least three documented contact attempts must be made on different days to the last available telephone number. If the subject is still unreachable after all contact attempts, they will be considered to be lost to follow-up (LTF). The site should document all attempts and LTF information in the trial database.

8 STATISTICAL CONSIDERATIONS

8.1 SAMPLE SIZE DETERMINATION

We anticipate randomizing, in an equal allocation ratio, a total of 40 participants with follow-up through at least 4 weeks, which will be the main time point for primary analysis.

For the primary test of engagement comparing standard vs. adapted digital CBT, the power calculation is based on the comparison of intervention groups for the main outcome of difference in usage days modules completed. Based on prior data (see preliminary data - Digital CBT in Medical Clinics), we would expect 50% less engagement for African Americans vs whites with our standard digital CBT app. Thus, to detect a 150% improvement in engagement related to adapted vs standard CBT for usage days (e.g 20 vs 10 usage days), with 80% power, a total of N=34 (n=17 per arm) is necessary. We are accounting for 10% attrition at 4 weeks.

8.2 POPULATIONS FOR ANALYSES

Our models will be based on an intent-to-treat principle as we will take measures to ensure limited dropout or non-adherence.

8.3 STATISTICAL ANALYSES

8.3.1 GENERAL APPROACH

All primary and secondary analyses will be preceded by descriptive analyses of baseline and clinical characteristics. Summary statistics will include means and standard deviations for continuous variables, and sample proportions for categorical variables. Median and interquartile range values will accompany continuous variables that are non-normal. Results will be presented for the entire sample and stratified by intervention arm. We will assess between-arm imbalance of baseline covariates by calculating standardized mean differences. For continuous variables, we will assess normality by visually inspecting univariate distribution via a normal probability plot. Transformations will be implemented if required.

8.3.2 ANALYSIS OF THE PRIMARY AND SECONDARY ENDPOINT(S)

Primary and Secondary Analyses. We will employ linear regression models for the primary outcome of usage days and the secondary outcome of techniques and sessions completed (Hypothesis 1) as a function of study arm (standard CBT vs. adapted CBT). We will account for multiple observations for each participant by including a random effect for subject. Additionally, baseline variables with clinically meaningful between-arm differences will be included as covariates.

Process evaluation. Change scores, baseline to 4 weeks, perceived stigma, relevance, relatability, will be tested as potential mediating variables. Contrasts will be estimated to assess the impact of standard and adapted CBT intervention on 4-week differences in perceived relevance, relatability, and stigma. We will then test whether lower perceived mental health

stigma and higher perceived program representativeness and relevance in the adapted CBT arm, mediates any observed group differences in engagement and program satisfaction.

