1.3 SCHEDULE OF ACTIVITIES

Schedule of interventions and of monitoring patient outcomes		Week of Study			
Outcome	Measure	1	2	3	4
Primary	Engagement: usage days, technique/sessions completed, log-ins, coach contacts				X
	Self-efficacy (SCSES)	X			X
	Mental Health Stigma/ SCD stigma	X			X
Process Evaluation	Perceived relevance and relatability			X	
	Depression (PHQ-9), Anxiety (GAD-7)	X	X	X	X
Quality of Life	Pain interference (PROMIS)	X			X
	Quality of life (ASCQ-Me)	X			X
Medical	Health care utilization: Opioid prescriptions, ED visits, hospitalizations				X

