2.3.3 ASSESSMENT OF POTENTIAL RISKS AND BENEFITS

While enrolled in the study participants will be given access to a health coach. Health coaches are trained personnel in dealing with individuals at risk, and are skilled at working with individuals at risk of feeling anxious or depressed. They will frequently assess participant risk and act accordingly.

Patients are able to stop the digital CBT program at any time, and we will frequently remind patients that they do not have to answer questions if it makes them uncomfortable.

Data Security

Coded data will be stored electronically and saved onto a separate secure database. Once the participant consents, the encrypted data is sent to a RedCap (or similar) secure server. There are two parts to the encrypted data that is transferred from the mobile device to the server: identifiable information upon enrollment and the non-identifiable study data. These two components are stored separately and linked by a unique identifier. The key linking these two are only accessible by the study staff.

This study involves the collection of data over the Internet using mobile devices. Although every reasonable effort will be taken, confidentiality during Internet communication procedures cannot be guaranteed and it is possible that additional information beyond that collected for research purposes may be captured and used by others not associated with this study

Patients will be encouraged to lock their device when not in use and to keep the latest security OS update. Patients will also be encouraged to avoid accessing untrusted sites.

This research is necessary to understand the feasibility of a mobile-technology-based behavioral intervention for mental health that predominantly targets a minority population.

Study endpoints

Primary Outcome Measures

Program engagement. Engagement will be measured by frequency and time on the app, number of lessons completed, and number of interactions (app messages) with health coaches over a 4-week period.

Secondary Outcome Measures

Pain Interference. The PROMIS Pain Interference Scale[86] is a validated questionnaire asking a patient how much day-to-day function is altered by pain. SCD impairs health-related quality of life (HR-QOL) more than most other chronic diseases. PROMIS is designed to allow streamlined, computer-aided administration, and has been tested in multiple populations and conditions including SCD.

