All participants will complete short surveys each week they are in the study. These surveys will be sent to their mobile phone as a web URL link. Each week, participants will complete a depression (PHQ-9) and anxiety (GAD7) symptoms questionnaire. At 1 and 4 weeks only, participants will also complete measures of Self-efficacy (SCSES), stigma, pain interference (PROMIS), and quality of life (ASCO-ME). In addition, as part of the intervention, participants are asked to interact with their assigned digital CBT program at least once per week if not more.

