4.4 END-OF-STUDY DEFINITION

Patients are considered to have completed the study once they have participated in weekly check-ins with a health coach during the 4 weeks and completed the assessments (STIG-9, SCSES, PROMIS, ASCQ-ME, PHQ-9, GAD-7) at the scheduled time points.

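### The process evaluation needs relevance and relatability change scores that one assessment cannot give, a stigma mediation conclusion that the timing cannot support, and a satisfaction outcome that nobody measures

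*Combined protocol and SAP*

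**What the plan says.** The process evaluation paragraph of Section 8.3.2 states: "Change scores, baseline to 4 weeks, perceived stigma, relevance, relatability, will be tested as potential mediating variables". It then plans between-arm contrasts at 4 weeks on relevance, relatability and stigma. Finally it tests whether lower stigma and higher representativeness and relevance in the adapted arm mediate arm differences in two outcomes, engagement and program satisfaction.

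The measurements available for this are set elsewhere:

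- In the Section 1.3 schedule, the row "Perceived relevance and relatability" has one mark, in the week 3 column as the table was extracted. The row "Mental Health Stigma/ SCD stigma" has marks at weeks 1 and 4.
- Section 4.1 agrees on stigma: "At 1 and 4 weeks only, participants will also complete measures of Self-efficacy (SCSES), stigma". Sections 6.1.2 and 7.3 repeat this.
- Section 4.4 defines completion as having "completed the assessments (STIG-9, SCSES, PROMIS, ASCQ-ME, PHQ-9, GAD-7) at the scheduled time points". That list has no relevance, relatability or satisfaction measure.
- Engagement is a total over the whole intervention period. The endpoint text in Section 2.3.3 includes the "number of interactions (app messages) with health coaches over a 4-week period", and Section 8.1 sets "follow-up through at least 4 weeks, which will be the main time point for primary analysis".
- Section 7.3 allows late forms: "Not completing questionnaires within 2 weeks of the due date is considered a missed follow-up".

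Section 8.3.9 calls secondary outcomes exploratory because of limited power. It does not mention the mediation tests.

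**The concern.** The stated rationale for the adaptation (Sections 2.1 and 4.1) is that stigma and lack of relatability hold engagement down. The process evaluation is the only planned analysis of that mechanism, and three parts of it do not fit the data to be collected.

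First, a change score needs two values, and relevance and relatability have one. Second, a mediator should act before the outcome it explains, but stigma is re-measured only when most or all of the engagement has already happened. Using a CBT app with a coach could itself lower stigma, and the planned test cannot tell this from lower stigma leading to more use. Third, an outcome with no measure cannot be analysed.

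At stake is the claim about mechanism that the pilot passes on to a larger trial. An analyst would have to improvise the relevance and relatability variables, and a positive stigma result could be reported as mediation when the design cannot show it.

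**Working it through.** No figure in the plan has to be reproduced for this point. The check compares the analysis text with the schedule and then illustrates the size of the time-order problem.

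**Step 1: what is needed and what is scheduled.** Week 1 is taken as baseline.

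| Variable in Section 8.3.2 | Values needed as planned | Values scheduled (Section 1.3) | Result |
|---|---|---|---|
| Relevance, relatability: change | 2 | 1 | Change cannot be computed |
| Relevance, relatability: arm contrast | 1 post-exposure | 1 | Can be computed; week to be reconciled |
| Stigma: change | 2 | 2 (weeks 1 and 4) | Can be computed |
| Program satisfaction | at least 1 | 0 | Cannot be analysed |

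The week 3 position comes from an extracted table and may have shifted. The first row of this comparison does not depend on it, because one mark in any column is still one value.

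**Step 2: timing of stigma against engagement.** The engagement window is 4 × 7 = 28 days. Week 4 covers days 22 to 28, so a week 4 form arrives with between 21/28 = 75% and 28/28 = 100% of the window elapsed. The 2-week allowance in Section 7.3 means that a form can also come after the window has closed. No stigma value falls between weeks 1 and 4, and Section 8.3.2 gives no engagement window that starts after the mediator is measured.

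**Step 3: how often reverse causation alone would look like mediation.** Apart from the sample size and attrition, the inputs are assumptions.

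- Completers: 40 × (1 − 0.10) = 36, or 18 per arm (Section 8.1).
- Arm effect on engagement: d = 0.98 SD. Section 8.1 gives 17 per arm and 80% power but no SD, alpha or sidedness. With an assumed two-sided alpha of 0.05, the normal formula gives d = (1.960 + 0.842) × √(2/17) = 0.96, and the noncentral t gives 0.99. The value 0.98 lies between them.
- Model: engagement E = 0.98 × arm + noise (SD 1). Stigma reduction S = r × E + √(1 − r²) × noise. Stigma responds to engagement only, so true mediation is zero.
- Test: called positive if both S on arm, and E on arm plus S (coefficient of S), have two-sided p < 0.05.

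In this model the arm-to-S path is 0.98r, and the coefficient of S given arm is r. The apparent mediated effect is therefore 0.98r², a share of 0.98r²/0.98 = r² of the arm effect. The rejection rates come from 40,000 simulated trials per setting.

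| Within-arm correlation r (assumed) | False mediation finding | Apparent share mediated, r² |
|---|---|---|
| 0.3 | about 5% | 9% |
| 0.5 | about 26% | 25% |
| 0.7 | about 51% | 49% |

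With r = 0 the rate is well under 1%.

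**The case against.** The strongest reply is that this is a process evaluation in a 40-person pilot and that Section 8.3.2 speaks only of potential mediators. Measuring mediator and outcome together is a common pilot limitation, usually handled with a caveat. That stands as an argument about severity, and it points to the same remedy. But the caveat is not in the plan: the tests sit in the primary and secondary analysis section, and Section 8.3.9 does not extend its exploratory label to them. A caveat would be needed even with better timing, since mediator and engagement could share common causes.

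A reader might infer that two of the three mediators cannot be computed. The documents do not support this. Only their change scores fail. The last sentence of the process evaluation paragraph compares levels between arms, for which one post-exposure score is enough.

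A reader might also infer that the planned 4-week contrast on relevance and relatability is an error. That is not established. A contrast needs one measurement, and if the table column shifted, the assessment may be at week 4. The two sections only need to agree.

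The lists of measures in Sections 4.1, 4.4, 6.1.2 and 7.3 are weak corroboration of the single assessment, because they omit even the one that is scheduled. The count rests on one row of the schedule. Other rows of that table kept several marks, so a lost mark is unlikely, and no other section adds a second assessment.

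Some naming is loose: representativeness stands where relatability stood, and the schedule lists two stigma constructs where Section 4.4 names one instrument. These are editorial matters and carry no weight here.

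**Conclusion.** The point holds in this form. As written, the change scores for relevance and relatability cannot be computed, and program satisfaction cannot be analysed. The stigma change can be computed and compared between arms, but its association with engagement cannot support a conclusion of mediation, because its only post-baseline value arrives with at least 75% of the engagement window elapsed.

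The first two conclusions rest on the schedule alone. The third rests on the timing and needs no simulation. The false-positive rates of about 5%, 26% and 51% show what reverse causation could do under the assumed effect and correlations. They do not show that it will occur, and the documents give no correlation from which to judge it.

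It would be wrong to read this as a threat to the trial's main result. The primary comparison of usage days by arm uses none of these variables. The consequence is confined to the claim about mechanism, so the change is worth making but not essential.

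**What to change.** 1. In Section 8.3.2, replace the change score for relevance and relatability with the single post-exposure score, compared between arms at the week in which it is actually scheduled. Reconcile Sections 8.3.2 and 1.3 on that week.
2. Keep the stigma change from week 1 to week 4 as an arm contrast. Label every analysis relating stigma, relevance or relatability to engagement an exploratory association, and state that no causal mediation claim will be made from it.
3. Remove program satisfaction as a mediated outcome. If it is wanted, add a few items to an existing web survey and enter them in the schedule.

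The cost is SAP wording and, if satisfaction is kept, a few survey items. No new visit is needed. The downside is a weaker claim about mechanism, which is the most that these measurements can support.

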8.3.4 PLANNED INTERIM ANALYSES

N/A. Analysis will be conducted at the end of week 4 after the study is complete.

8.3.5 ADDRESSING MISSING DATA

We will minimize missing data by use of a paperless data collection system and by contacting participants when data are not entered in a timely fashion. We will attempt to characterize the mechanism of missingness (missing completely at random, missing at random, or not missing at random) by comparing rates of missingness/attrition between study arms. Additionally, we will compare baseline characteristics between participants with and without missing outcome data. If we conclude that our missingness is random, then our likelihood-based approach for the primary analyses will address this. Otherwise, if the missingness can be characterized as non-ignorable (not missing at random), we will use approaches such as joint modeling or shared parameter models to produce unbiased estimates of treatment effects. All reasons for dropout or other missing values will be entered by research staff or community groups (if encountering the patient during community activities), tabulated and summarized, and results will be reported using the Consolidated Standards of Reporting Trials (CONSORT) diagram. Patients who stop reporting data in the app will receive inquiry text messages or a phone call.

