6.3 MEASURES TO MINIMIZE BIAS: RANDOMIZATION AND BLINDING

Randomization: Participants will be randomized in an equal fashion (1:1) to both study arms. Random permuted block randomization will be used to create an allocation list that will be integrated within our Web-based data entry system.

Reduce the potential for bias. The introduction to both interventions will look identical and participants will not be told what type of training they are receiving. We will make every effort to mask the intervention type; however, as with all behavioral interventions, completely blinding participants to the intervention is challenging. The investigative team will continue to maintain clinical equipoise regarding the comparative therapeutic merits of each treatment. Randomization will avoid selection bias as well as volunteer or referral bias. A dropout analysis will be carried out to determine the contribution of attrition bias. All outcomes measures will be collected electronically, without an interview, to avoid expectation bias. We have also found this mode of data collection to be superior to assessments by phone for timely follow-up.

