8.3.6 SUB-GROUP ANALYSES

Planned sensitivity analyses to determine the impact of key assumptions. The major assumption is that patients will complete the intervention program to which they are randomly assigned. Although we have implemented several methods to promote engagement and limit dropout (e.g., health coaches[94]), digital interventions often experience high attrition over time with few participants completing all assigned modules.[95] We will track the reasons for non-completion and seek patterns (e.g., moved away, died, started working and became too busy, people with higher cognitive level lost interest) that are amenable to statistical analysis of the missing data. Sensitivity to this assumption can be determined by comparing analysis by three levels of participation in the intervention: enrollment and intervention assignment (Intent-to-Treat), participation in at least half the intervention, and zero participation in the intervention. Propensity score methods could also be used to deal with missing data. We will also test for differences in retention by recruitment site (e.g., community vs. clinical).

The comparative effectiveness trial with two active arms might show that both interventions work moderately well, which means there might not be superiority for the entire population. One intervention might be more suitable for certain subgroups of patients, so our Aim 2 analysis of primary and secondary outcomes by mental health subgroup should provide valuable information on suitability of the intervention for different subgroups.

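### The missing-data model is chosen from checks that cannot separate MAR from MNAR, and the participation-level sensitivity analysis would condition on the outcome if applied to engagement

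*Combined protocol and SAP*

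**What the plan says.** Section 8.3.5 sets out to attempt to classify missingness as MCAR, MAR or MNAR. It names two checks: "by comparing rates of missingness/attrition between study arms", and "we will compare baseline characteristics between participants with and without missing outcome data". The result selects the model. On one branch, "If we conclude that our missingness is random, then our likelihood-based approach for the primary analyses will address this". On the other, if missingness is judged non-ignorable, "we will use approaches such as joint modeling or shared parameter models to produce unbiased estimates of treatment effects". Reasons for dropout are recorded, tabulated and reported in the CONSORT diagram, but the branch rule gives them no role.

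Section 6.3 adds: "A dropout analysis will be carried out to determine the contribution of attrition bias".

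Section 8.2 sets the analysis population: "Our models will be based on an intent-to-treat principle". Section 8.3.6 then takes program completion as the major assumption and says: "Sensitivity to this assumption can be determined by comparing analysis by three levels of participation in the intervention". The levels are intent-to-treat, "participation in at least half the intervention, and zero participation in the intervention". No outcome is named, none is exempted, and half is not defined. Section 8.3.2 makes usage days the primary outcome and techniques and sessions completed the secondary one.

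**The concern.** The two parts are related but separate.

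First, the difference between MAR and MNAR concerns how missingness relates to values nobody has seen. A comparison of observed arms and baseline variables carries no information on that. The plan nevertheless lets such a comparison decide which model is fitted, after the data are in. If the team concludes that missingness is random, the plan asks for no analysis under MNAR. If it concludes otherwise, the plan expects unbiased estimates from models that are unbiased only when their own untestable dropout model is right. For the same reason, the attrition comparisons in Sections 8.3.5 and 8.3.6 describe who left, but cannot by themselves measure the attrition bias that Section 6.3 says will be determined.

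Second, in most trials participation is an exposure and the outcome is something else. Here app use is the primary outcome. Splitting participants by how much of the program they used, and then comparing usage days or sessions, selects on the outcome. A real engagement benefit could then be reported as not robust.

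**Working it through.** **Planning figures (Section 8.1).** 40 randomized 1:1 gives 20 per arm; 10% attrition is 4 of 40. N=34 inflated for 10% attrition is 34/0.90 = 37.8, so 38, which 40 covers. No SD or alpha is stated. With a two-sided 5% t-test (assumed), 17 per arm at 80% power corresponds to a standardized difference of 0.991. The example of 20 vs 10 usage days then implies an SD of 10/0.991 = 10.1. The point does not depend on these figures; they only set a realistic scale.

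**What the checks can show.** Let R be missing status, A arm, X baseline and Y the outcome. The first check estimates P(R | A); the second compares X between the two values of R. Dependence of R on A or X is evidence against MCAR, but is still MAR if the model conditions on A and X. Absence of such dependence does not exclude dependence of R on the unseen Y. Neither result bears on MAR against MNAR.

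A simulation shows this: 20 per arm, 10% missing, 5,000 runs. Assumed inputs are a baseline-outcome correlation of 0.5, a logistic missingness slope of 1.5 and, for MNAR, missingness driven by the outcome residual in opposite directions by arm. The benchmark is a 5% test.

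| Mechanism | Arm check flags | Baseline check flags | Bias of adjusted estimate (SD) |
|---|---|---|---|
| MCAR | 1.2% | 4.5% | about 0 |
| MAR | 1.2% | 62% | about 0 |
| MNAR | 1.2% | 5.0% | +0.19 |

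The checks react to the harmless mechanism and look the same under MCAR and under the harmful one. The size of the bias follows from the assumed inputs.

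**Size on a questionnaire.** If missing PHQ-9 scores in one arm are worse than MAR predicts by d points, the arm difference moves by (fraction missing in that arm) × d. With d = 5 (assumed): 2/20 × 5 = 0.5 points; 4/20 × 5 = 1.0 point.

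**Participation levels applied to usage days.** At the zero level every value is 0 in both arms, so the difference is 0 − 0 = 0 whatever the truth. For the half level, assume days of use out of 28 follow a beta-binomial distribution with means 10 and 20 (Section 8.1), equal SD in both arms, and half read as at least 14 days. The table gives the exact share kept and the mean among those kept.

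| Assumed SD | Standard: kept, mean | Adapted: kept, mean | Difference (true 10) |
|---|---|---|---|
| 6 | 28%, 17.8 | 84%, 22.0 | 4.2 |
| 8 | 33%, 19.9 | 77%, 23.7 | 3.8 |
| 10 | 35%, 22.4 | 73%, 25.5 | 3.1 |

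The cut removes most of the standard arm and keeps only its heaviest users. If half instead means use in at least 2 of the 4 weeks, the same model gives about 9.4, 8.3 and 7.1 days. The undefined word therefore drives the result.

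**The case against.** The strongest reply is that the first part has little to act on. Section 8.3.5 ties its rule to the primary analyses, and those concern app use. Under ITT a participant who stops using the app most naturally contributes no further days rather than a missing value, so missing primary data should be rare. The questionnaires, where data will be missing, are exploratory in a 40-person pilot. The plan also names MNAR models, records dropout reasons and says only that it will attempt to characterize the mechanism. This stands as a limit on impact. It does not rescue the rule, which still makes the MNAR models depend on a conclusion the data cannot give.

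A power argument against the checks would be weak. The plan sets no significance threshold for them, and Section 8.3.1 assesses between-arm baseline imbalance by standardized differences. It would also be beside the point, since a larger sample would not separate MAR from MNAR either.

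On the second part, Section 8.3.6 says sensitivity can be determined this way, not that it will be, and its later talk of comparative effectiveness fits symptom outcomes. That is fair: no section applies the levels to usage days. The concern is conditional, but nothing excludes that use and the primary outcome is app use. The sizes also depend on the model. At SD 10 the beta-binomial puts about 40% of the adapted arm at all 28 days and about 25% of the standard arm at none, which may not be realistic.

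A reader might infer that the dropout analysis promised in Section 6.3 is nowhere described. The documents do not support that: Section 8.3.5 describes comparisons by arm and baseline and a tabulation of reasons, and Section 8.3.6 adds retention by recruitment site. The fault is that these cannot quantify bias, not that they are absent.

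**Conclusion.** The point holds, at a level between minor and should-fix.

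The model choice in Section 8.3.5 rests on a distinction its checks cannot make, and one branch leaves MNAR unexamined. This is a matter of logic and needs no assumed figures. Its practical weight is modest: 0.5 to 1.0 PHQ-9 points under an assumed 5-point shift with 2 to 4 of 20 missing in one arm, on an exploratory outcome. That rests on usage days being near complete, which the documents suggest but do not state.

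If the levels in Section 8.3.6 are applied to engagement, the zero level is uninformative by construction and the half level is truncated. The loss from 10 days to roughly 3 to 4 depends on the 28-day window, the distribution, the SD and the 14-day cut, all assumed; only the direction is general.

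A reader might go further and conclude that the primary engagement result is compromised. The documents do not support that, because ITT remains the primary estimate and the participation levels are only a sensitivity analysis. The exact definition of usage days and the subject random effect in Section 8.3.2 are a separate clarification and not part of this conclusion.

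**What to change.** In Section 8.3.5, replace the branch with a fixed plan, for example:

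> Outcomes with missing values will be analysed under MAR with the likelihood-based model. Robustness to MNAR will be assessed whatever the observed pattern, by shifting missing values over a prespecified range in each arm and/or by joint or shared-parameter models fitted as sensitivity analyses. Missingness by arm, baseline comparisons and reasons for dropout will be reported descriptively and will not select the model.

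The joint and shared-parameter models already named can stay. What changes is that they no longer depend on the checks and are no longer described as giving unbiased estimates without conditions. This analysis can also serve the purpose stated in Section 6.3.

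In Section 8.3.6, add:

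> The participation-level comparison will not be applied to usage days, modules or other engagement outcomes. For other outcomes it is descriptive, with half the intervention defined as [prespecified measure and cut].

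The cost is protocol wording and one sensitivity table. No change to sample size, data collection or the ITT estimate is needed.
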